5.1.1 Exploratory genomic analyses

During this study, subjects will also have the option of providing additional informed consent for exploratory genomic (DNA and RNA) analyses. Participation in this additional portion of the Line not consented to Line not consented to Line in as tollows: For DNA: Blood samples will be collected at Baseline (Visit 2), at Visit 8, and prior to the last dose of IMP (Visit 13). For RNA: Blood samples will be collected at Baseline (Visit 2) at Visit last dose of IMP (Visit 13), and at the FV (Visit 20) For each DNA blood study is optional and does not preclude subject's eligibility for participation in the main study.

a volume of 2.5mL whole blood is needed.

Any exploratory biomarker or genomic analysis will only ever be related to the exploration of the underlying causes of MG in patients, related biology, and drug response. Justification for additional genomic analyses is detailed in Section 5.4.3.

Details on the collection, storage, preparation, and shipping of samples will be presented in the Laboratory Manual provided separately.

Any results from this analysis will be reported separately and will not form a part of the main clinical study report.

Study duration per subject 5.1.2

The maximum duration of the study per subject will be approximately 18 weeks, consisting of the following 3 periods:

Screening Period: 1 to 28 days

Treatment Period: 6 weeks

Observation Period: 8 weeks

The end of the study is defined as the date of the final clinic/hospital or home visit of the final subject in the study.

5.1.3 Planned number of subjects and sites

To ensure that at least 40 subjects are evaluable for the primary efficacy variables, a sample size of approximately 42 randomized subjects is planned at approximately 30 sites to achieve the targeted number of 40 evaluable subjects.

Anticipated regions and countries

It is planned to recruit subjects in USA, Canada, and Europe in this study, with possible extension to other regions and countries.

5.1.4

REPACTOR CONTRACTOR OF THE CON

Table 5.1: Schedule of assessments

Clinical Study F	rotocol								UCE	37665	5											MG000
Table 5.1:	Sche	edule of	ass	essm	ents	5															ionsti	
Assessments	Screen	ing	Trea	tment I	Period											Obs	serva	tion F	Period	L adic	7	UV
		r	Dosi	ng Peri	od 1		1			Dos	ing Pei	iod 2	n	I	r		I		05	•		
	Visit	1	2 BL	3 ^b	4	5 ^b	6	7 ^b	8	9	10 ^b	11	12 ^b	13	14 ^b	15	16	J.	18	19	20 FV/PEOT c	
	Day	-28 to -1	1													500	57	64	78	92	99	
				$ \begin{array}{c ccc} (\pm 2 \\ days) \end{array} \begin{pmatrix} (\pm 2 \\ days) \end{pmatrix} $													(± 2	days)			$(\pm 2 \text{ days})$	
Written informed	consent	Х											×.	lor	 							
Written informed for genomic subst		Х								Ċ	182		2P/100									
Demographic data		Х							\sim	\sim		5										
Verification of ind exclusion criteria		Х	Х						ACT Y		122											
Call or enter IRT register the visit	to	Х			Х		Х	X		Jill		Х		Х							Х	
Call or enter IRT/ Randomization	r		X						x etims	Х												
Withdrawal criter	ia		Х	Х	Х	Х	Х	XC	X	Х	Х	Х	Х	Х	Х	Х	Х	Х	Х	Х		
General medical/ procedures history	y	Х					X	\mathcal{T}														
Prior and concom medication	itant	Х	Х	Х	x	XQ	X	Х	Х	Х	Х	Х	Х	Х	Х	Х	Х	Х	Х	X	Х	X
Concomitant med procedures	ical		Х	e	×® >		Х		Х	Х		Х		Х		Х	Х	Х	Х	Х	Х	X
Vital signs ^f		Х	Х	2 150	Х		Х		Х	Х		Х		Х		Х	Х	Х	Х	Х	Х	X
Body weight, heig		Х	, v v							Х											Х	
Recording of AEs		x	X	Х	Х	Х	Х	Х	Х	Х	Х	Х	Х	Х	Х	Х	Х	Х	Х	Х	Х	X
Confidential	15 docu	nent	X X 							Table 5.1: Schedule of assessments

UCB Clinical Study P	rotocol								UCE	37665	5										L'ere	Sep 2017 MG0002
Table 5.1:	Sche	edule of	ass	essm	ents	5														4	iions th	
Assessments	Screen	ing	Trea	atment I	Period											Obs	serva	tion P	eriod	$-\cdot$		UV
			Dosi	ing Peri	od 1	l	1		1	Dos	ing Pe	iod 2		I	r		I	6	5			
	Visit	1	2 BL	3 ^b	4	5 ^b	6	7 ^b	8	9	10 ^b	11	12 ^b	13	14 ^b	15	16	9	18	19	20 FV/PEOT c	
	Day	-28 to -1	1	2	8 ^d	9	15 ^d	16	22 ^d	29 ^d	30	36 ^d	37	43 ^d	44	50	57	64	78	92	99	
				$ \begin{array}{c c c c c c c c c c c c c c c c c c c $													(± 2	days)			$(\pm 2 \text{ days})$	
Full physical examination		Х		days) uays) uays) days) days)																	Х	
Brief physical examination			Х							x	18-		oplico									
Full neurological examination ^h		Х									i.	5									Х	
Brief neurological examination	l		Х						DACI	X	Sille											
Query for suicidal	lity ⁱ	Х	Х		Х		Х	\$	X	X		Х		Х		Х	Х	Х	Х	Х	Х	Х
12-lead ECG ^j		Х	Х		Х		Х		X	Х		Х		Х		Х			Х		Х	
Laboratory tests (hematology, cher urinalysis)	nistry,	Х	Х		Х		x	24	X	Х		Х		Х		Х	х		Х		Х	
Serology testing f Hepatitis B, and F C	or HIV, Iepatitis	Х				199	s															
IGRA tuberculosi	s test ^k	Х			~°°																	
Tuberculosis Sign Symptoms question		Х		USOC																	Х	
Blood sampling fo of UCB7665 ¹	or PK		X C		Х		Х		Х	Х		Х		Х		Х						
		nent car	X X																			
Confidential	20CU								Page 2	6 of 1	93											

Table 5.1: Schedule of assessments

Assessments	Screen	ing	Trea	atment I	Period	l										Obs	servat	ion P	Period	a de la companya de l		UV
			Dosi	ing Peri	od 1					Dos	ing Per	riod 2							6			
	Visit	1	2 BL	3 ^b	4	5 ^b	6	7 ^b	8	9	10 ^b	11	12 ^b	13	14 ^b	15	16	Jan Star	18	19	20 FV/PEOT c	
	Day	-28 to -1	1	2	8 ^d (± 2 days)	9	15 ^d (± 2 days)		22^d (± 2 days)	29^d (± 2 days)	30	36^d (± 2 days)	37	43^d (± 2 days)	44	50	5 7 (± 2 d	64 days)	78	92	99 (± 2 days)	
Blood sampling fo analysis sub-study			х						Х					X	6							
Blood sampling fo analysis sub-study	or RNA m		х		х				х	C C	122	3.	29/100	х							х	
Serum pregnancy	test	х								\rangle	j.	5										
Urine pregnancy t	est ⁿ		х		х		х		x	х	12	х		х		х	х	х	х	х	Х	
Administration of	IMP		Х		х		х	<	Q ^r	X)	Х		х								
			х		х		x	Ŷ	x	X		х		х		х	х	х	х	х	х	
Serum complement (C3,C4) and plasm complement level and C5a) ⁰	na		х		x		x	4	aller	х		х		х							Х	
Immunoglobulins IgG and IgG subc		х	х		х		x		х	Х		х		х		х	х	Х	х	х	Х	
gA, IgM, IgE			х		Ċ	24			Х	х		х		х		х	х				Х	
MG-specific autoantibodies			х	Sec	x					Х		х				х					Х	
		mentican	10°10	ల్																		
Confidential	20CU								Page 2	7 of 1	.93											

Table 5.1: Schedule of assessments

Assessments	Screen	ing	Trea	ntment F	Period	I										Ob	serva	tion I	Period	a di la	7	UV
			Dosi	ing Perio	od 1					Dos	ing Per	riod 2							6	1-		
	Visit	1	2 BL	3 ^b	4	5 ^b	6	7 ^b	8	9	10 ^b	11	12 ^b	13	14 ^b	15	16	J.S.	18	19	20 FV/PEOT c	
	Day	-28 to -1	1	2	8 ^d (± 2 days)	9	15 ^d (± 2 days)	16	22^d (± 2 days)	29^d (± 2 days)	30	36^d (± 2 days)		43^d (± 2 days)	44	50	5 7 (± 2	64 days)	78	92	99 (± 2 days)	
Blood sampling fo exploratory bioma analysis			х		x		X		х	x	L	x		X	0			х		x		
Blood sampling fo safety biomarker analysis: may inclu- not limited to			х		х		х	R	x DACTE		8 5112311	x		Х		х	х	х	х	х	Х	
BAFF analysis			х		х		х		x	х		х		х				х		х		
Cytokines ^q			х				х		Sit	х				х							х	х
Vaccination-speci antibody titers	fic	х					K de	2													Х	
MG-composite sea	ale ^r	х	х		x	'6 6,	x		х	х		х		х		х	х	х	х	х	Х	
QMG scale ^s		х	х		X		х		х	х		х		х		х	х		х		Х	
Muscle weakness severity and fatiga scale	bility		x	e JSec	x		х		х	х		x		х		х	х	х	х	х	х	
Fatigue scale		h.	Ň		х		х		х	х		х		х		х	х	х	х	х	х	
MGADL scale		ar	x							х						х		х			Х	
Confidential	is docu	nentco							Page 2	8 of 1	193											

Table 5.1: Schedule of assessments

Assessments	Screen	ing	Trea	tment F	Period	l										Obs	serva	tion P	eriod	a di la	· · · · · · · · · · · · · · · · · · ·	UV
			Dosi	ng Perio	od 1					Dos	ing Per	riod 2							0	-		
	Visit	1	2 BL	3 ^b	4	5 ^b	6	7 ^b	8	9	10 ^b	11	12 ^b	13	14 ^b	15	16	Br	18	19	20 FV/PEOT	
	Day	-28 to -1	1	2	8 ^d	9	15 ^d	16	22 ^d	29 ^d	30	36 ^d	37	43 ^d	44	500	57	64	78	92	99	
					(± 2 days)		(± 2 days)		$(\pm 2 \text{ days})$	(± 2 days)		(± 2 days)		(± 2 days)	200		(±2	days)	I		$(\pm 2 \text{ days})$	
MGII			Х				Х			Х				X	5		Х		Х		Х	
MGFA classificati	ion	Х	Х							Х	. 1		Š.								Х	
Jitter (SFEMG) measurement ^t			Х							x	8	S.	28/10									
Headache question	nnaire ^u		Х	Х	Х	Х	Х	Х	x	$X_{\rm X}$	X	рх	Х	Х	Х	Х	Х	Х	Х	Х	Х	Х
Stool sample asses	ssment ^v		Х		Х		Х		X	X	il.	Х		Х		Х	Х	Х	Х	Х	Х	Х
Subject exit interv	iew							2		J'll											Х	

AE=adverse event; BAFF=B-cell activating factor; BL=Baseline; BP=blood pressure; CSF=cerebrospinal fluid; CT=computed tomography; DNA=deoxyribonucleic acid; ECG=electrocardiogram; FV=Final Visit; GI=gastrointestinal; HIV=human immunodeficiency virus; IgA=immunoglobulin A; IgE=immunoglobulin E; IgG=immunoglobulin G; IGRA= interferon-gamma release assay; IgM=immunoglobulin M; IMP=investigational medicinal product; IRT=interactive response technology; LP=lumbar puncture; MG=myasthenia gravis; MGADL=myasthenia gravis-Activities of Daily Living; MGFA=Myasthenia Gravis Foundation of America; MRI=magnetic resonance imaging; PEOT=premature end of treatment; PK=pharmacokinetics; PR=pulse rate; RNA=ribonucleic acid; QMG=Quantitative Myasthenia Gravis; B; SFEMG=single fiber electromyogram; TB=tuberculosis; UV=Unscheduled Visit

^a Subjects will return to the clinic/hospital for Visits 15, 16, 18, and 20; for Visits 17 and 19 subjects will either return to the clinic/hospital, or, if possible and agreed by both the investigator and subject, have home visits conducted by certified healthcare professionals.

^b This visit is a telephone contact 24 hours post-IMP dose start.

^c Subjects who withdraw early will be encouraged to complete the PEOT Visit plus the FV (approximately 8 weeks after the final study drug administration).

^d A visit window of ± 2 days is allowed for the dosing visits. The visit window of ± 2 days is relative to the first dosing visit date. However, there should be a minimum interval of 5 days and maximum interval of 9 days as compared to the previous dose.

^e Includes consent for jitter (SFEMG) for the subjects consenting to this measurement at the participating sites. Additional informed consent is needed for participation in the exploratory genomic substudy.

^f Systolic and diastolic BP, pulse rate, temperature, and respiratory rate. On dosing days, vital signs will be measured prior to IMP administration, 15 minutes after the start of the infusion, at the end of the infusion, 2 hours after the end of infusion and 4 hours after the end of the infusion. At nondosing visits, vital signs need only be taken once during the visit.

Confidential

Page 29 of 193

- ^g Body weight at Screening and at Visit 9 will be used for calculation of dose; height will be assessed only at Screening.
- ^h In addition to Screening and the FV, a full neurological examination should be performed for any subject who experiences severe headache.

- ^u This assessment is applicable only to subjects experiencing severe headaches and will be performed daily until resolution (ie, if headache becomes moderate or mild, normal collection of AEs should apply); this assessment will be followed by a neurological assessment (including fundoscopy). Additionally, other diagnostic procedures including but not limited to CT scan, MRI and/or LP for CSF collection to be performed if indicated at the discretion of the investigator.
- ^v Stool collection and analysis will be performed for subjects reporting moderate or severe diarrhea. The frequency of stool sampling will be as clinically indicated in the opinion of the investigator. Analysis of stool samples will be performed locally.

[figure not shown]
	N. OS	3
	SUPPO	
	Sed to	
	then	
×ď	anne	
Confidential	annot be used to support an	Page 30 of 193
THIS		

15 Sep 2017 MG0002

5.3 Schematic diagram

Figure 5.1 presents a schematic diagram of the study design.

Figure 5.1: Schematic diagram

Rationale for study design and selection of dose 5.4

Choice of study design and endpoints 5.4.1

The primary objective of the study is to evaluate the clinical efficacy of UCB7665 as a chronic-intermittent treatment for subjects with moderate to severe generalized MG. Additionally, this study will provide data for future study planning, whether for chronicintermittent treatment or a longer therapy option by evaluating the general concept that UCB7665 has a clinical effect in patients with generalized MG.

During the first Treatment Period, a 2-arm parallel design study will allow comparison of the change from Baseline in QMG score to Visit 9 (Day 29) between UCB7665 7mg/kg and placebo.

The choice of the primary efficacy outcome measures and the timing of approximately 4 weeks after the first dose of study drug are predicted to be the optimal approach to measure improvements based on effect seen in other therapies and recommendations of the Scientific Advisory Board of the MGFA (Barth 2013; Benatar 2012; Howard 2013). Then the second Dosing Period with a rerandomization allows for additional supportive data to be evaluated as well as offering the placebo subjects a chance to receive UCB7665.

Each subject will be asked to participate up to a maximum of approximately 18 weeks, consisting of a Screening Period (14 to 28 days), Treatment Period (6 weeks) and an Observation Period (8 weeks). The Treatment Period will consist of Dosing Period 1 followed by Dosing Jung/kg or Jung/kg in Dosing Period 1 followed by Jung Period 2. Jung Period 2. Jung Period 2. Group 3: Subjects will receive 3 weekly doses of placebo in Dosing Period 1 followed by 3 weekly doses of 7mg/kg in Dosing Period 2. Group 4: Subjects will receive 3 weekly doses of placebo in Dosing Period 1 followed by 3 weekly doses of 4mg/kg in Dosing Period 2. Group 4: Subjects will receive 3 weekly doses of placebo in Dosing Period 1 followed by 3 weekly doses of 4mg/kg in Dosing Period 2. Group 4: Subjects will receive 3 weekly doses of placebo in Dosing Period 1 followed by 3 weekly doses of 4mg/kg in Dosing Period 2. All subjects participating in Dosing Period 2. Period 2. Dosing Period 1 will have 2 parallel Treatment Groups (UCB7665 7mg/kg or placebo)

change from Baseline in QMG score compared to placebo at Visit 9, will be assessed for subjects treated with 7mg/kg UCB7665 vs subjects treated with placebo in Dosing Period 1. The comparison of the change from Baseline in QMG score at Visit 16 in Group 3 will strengthen analyses of the results of the primary outcome measure in Group 1. Because subjects in both Group 1 and 2 will be dosed for 6 times over 6 weeks, the data from these subjects will inform safety and the development of ADAs with extended dosing durations. Data regarding dose response and the time to clinical and PD response from Group 3 (7mg/kg) vs. Group 4 (4mg/kg) in the second Dosing Period will be able to be compared. Furthermore, safety and efficacy data from Group 2 in particular will provide information addressing the concept of treating subjects with a higher "loading" dose and then maintaining them on a lower dose regimen.

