- Dosing Period 1 will be 4 weeks, with 2 parallel Treatment Groups (UCB7665 7mg/kg or placebo).
- Dosing Period 2 will be 2 weeks, with 2 parallel Treatment Groups (UCB7665 7mg/kg or UCB7665 4mg/kg).

variations thereof Prior to receiving an infusion with IMP, subjects will be assessed for efficacy measurements at each visit in the Treatment Period. For all safety and efficacy measurements, the order specified in the Study Procedures Manual is recommended to be used as a guide.

Dosing Period 1: Dosing Period 1 will last for approximately 4 weeks (Day 1 to Day 28) and includes Visits 2, 3, 4, 5, 6, 7, and 8. Following completion of the Screening Period, eligible subjects will check-in at the clinic/hospital for the Randomization Visit (Visit 2). Subjects who continue to meet eligibility requirements will be randomized 1:1 to receive 7mg/kg of UCB7665 or placebo, administered by an approximately 30 minute sc infusion at weekly intervals for 3 weeks (Visits 2, 4, and 6) followed by an assessment visit at Week 4 (Visit 8). At Visits 2, 4, and 6 in Dosing Period 1, subjects will be required to remain in the clinic/hospital for at least 4 hours for safety monitoring after the infusion. Subjects may leave the clinie/hospital once the safety monitoring postdose period is over and the investigator or designee has no safety concerns. A follow-up telephone call will be conducted 24 hours postdose to assess the status of the subject (Visits 3, 5, and 7). Subjects will return to the clinic/hospital at Visit 8 for safety and efficacy assessments (see Section 5.2, Schedule of Study Assessments). The primary efficacy endpoint, change from Baseline in the QMG score, will be assessed at the beginning of Dosing Period 2 at Visit 9 (Day 29) prior to rerandomization. The efficacy assessments that are performed at Visit 9 will therefore occur 2 weeks after the final dose of study drug in Dosing Period 1.

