Dosing Period 2: Dosing Period 2 will last for approximately 2 weeks (Day 29 to Day 43) and includes Visit 9, 10, 11, 12, 13, and 14. Subjects will return to the clinic for Visit 9, 11, and 13 for safety and efficacy assessments (see Section 5.2, Schedule of Assessments) in the order specified in Section 8. At Visit 9, following the administration of safety and efficacy assessments, subjects initially randomized at Baseline to placebo or to 7mg/kg of UCB7665 will be rerandomized 1:1 to receive either 3 doses of 7mg/kg or 3 doses of 4mg/kg administered by a 30 minute sc infusion at weekly intervals (Visit 9, 11, and 13). The interactive response technology (IRT) will stratify the rerandomization based on the treatment received in Dosing Period 1 (see Section 7,10 for further details regarding randomization). At each weekly clinic visit in Dosing Period 2 (Visits 9, 11, and 13), subjects will be required to remain in the clinic/hospital for at least 4 hours safety monitoring postdose period as determined. Subjects may leave the clinic/hospital once the safety monitoring postdose period is over and the investigator or designee has no safety concerns. A follow-up telephone call will be conducted 24 hours postdose to assess the status of the subject (Visits 10, 12, and 14).

Observation Period: All subjects must be followed for 8 weeks after the final dose of IMP is administered. Subjects will return to the clinic for Visits 15, 16, 18, and 20 for efficacy and for safety assessments (see Section 5.2, Schedule of Assessments). Subjects will either return to the clinic/hospital, or, if possible and agreed by both investigator and subject, have home visits conducted by certified healthcare professionals, for Visits 17 and 19. The Observation Period begins the day after the final dose of IMP (ie, Visit 13, Day 43); Visit 15 (Day 50) is the first visit in the Observation Period.

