1 INTRODUCTION

The purpose of this statistical analysis plan (SAP) is to provide all information that is necessary to perform the required statistical analysis of MG0002. It also defines the summary tables, figures and listings (TFLs) to be included in the final Clinical Study Report (CSR) according to the protocol.

This SAP is based upon, and assumes familiarity, with the following study documents:

1. Final Protocol: 21 Oct 2016
2. Protocol Amendment 1: 07 Feb 2017
3. Protocol Amendment 2: 15 Sep 2017

Unless specified below, the study will be analyzed as described in the most recent version of the protocol/amendment (European Union Drug Regulating Authorities Clinical Trials [EudraCT]-Number: 2016-002698-36).

If a future protocol amendment necessitates a substantial change to the statistical analysis of the study data, this SAP will be amended accordingly. If, after database lock, additional analyses are required to supplement the planned analyses described in this SAP, those unplanned analyses will not be described in an amended SAP but they will be described in a separate statistical analysis plan. However, if analysis definitions have to be modified or updated, a SAP amendment will be required. The content of this SAP is compatible with the International Council for Harmonisation (ICH)/ Food and Drug Administration (FDA) E9 Guidance documents. UCB is the sponsor and PAREXEL International is the Contract Research Organization (CRO) for this study.

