Dosing Period 2: Dosing Period 2 will last for approximately 2 weeks (Day 29 to Day 43) and includes Visit 9, 10, 11, 12, 13, and 14. Subjects will return to the clinic for Visit 9, 11, and 13 for safety and efficacy assessments. At Visit 9, following the administration of safety and efficacy assessments, subjects initially randomized at Baseline to placebo or to 7mg/kg of UCB7665 will be rerandomized 1:1 to receive either 3 doses of 7mg/kg or 3 doses of 4mg/kg administered by a 30 minute sc infusion at weekly intervals (Visit 9, 11, and 13). The interactive response technology (IRT) will stratify the rerandomization based on the treatment received in Dosing Period 1. At each weekly clinic visit in Dosing Period 2 (Visits 9, 11, and 13), subjects will be required to remain in the clinic/hospital for at least 4 hours safety monitoring postdose period as determined. Subjects may leave the clinic/hospital once the safety monitoring postdose period is over and the investigator or designee has no safety concerns. A follow-up telephone call will be conducted 24 hours post dose to assess the status of the subject (Visits 10, 12, and 14).

Observation Period: All subjects must be followed for 8 weeks after the final dose of IMP is administered. Subjects will return to the clinic for Visits 15, 16, and 18 for efficacy and for safety assessments. Subjects will either return to the clinic/hospital, or, if possible and agreed by investigator and subject, have home visits conducted by certified healthcare professionals, for Visits 17, 19, and 20. The Observation Period begins the day after the final dose of IMP (ie, Visit 13, Day 43); Visit 15 (Day 50) is the first visit in the Observation Period.

Figure 2–1 presents a schematic diagram of the study design.

Figure 2–1: Schematic diagram

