3.3 Definition of Baseline values

Baseline will be the last available predose value prior to the first infusion of study drug in Dosing Period 1, or if missing, the Screening values. Scheduled or unscheduled measurements can be used as the Baseline value. Expected measurement-specific Baseline time points are presented in Table 3–1. If an unscheduled measurement occurs after the planned baseline measurement time point but before dosing, then the unscheduled measurement will be used.

Table 3–1: Expected Baseline Visits

Measurement	Baseline
Safety data 
 • Clinical Chemistry • Hematology • Urinalysis • ECG • Vital signs • [REDACTED] • [REDACTED] • [REDACTED] • Body weight 	
 • Clinical chemistry, Hematology, Urinalysis, ECG and Vital signs: Predose Day 1 or if missing the Screening value • [REDACTED] [REDACTED] [REDACTED]: Predose Day 1 • Body weight: screening visit

Table 3–1: Expected Baseline Visits

Measurement	Baseline
Pharmacodynamic data 
 Total serum IgG Serum IgG subclass concentrations MG specific antibodies (██████████) 	
 Total serum IgG and Serum IgG subclass: Predose Day 1 or if missing the Screening value Mg-specific autoantibodies: Predose Day 1
Immunological data: 
 IgM, IgE, IgA Serum complement levels (C3 and C4) and plasma complement levels (C3a and C5a) ██████████ Serum BAFF levels Cytokines ██████████ specific IgG antibodies Exploratory biomarkers relating to mechanism of action, disease activity, treatment response, and clinical outcome 	
 IgM, IgE, IgA, C3, C4, C3a, C5a, ██████████, BAFF, cytokines: Predose Day 1 ██████████ antibodies: Screening Exploratory biomarkers: Predose Day 1
Efficacy data: 
 QMG scale MG-composite scale MGADL MGFA scale MG muscle weakness Fatigue MGII SFEMG 	
 QMG, MG composite scale and MGFA: Predose Day 1 or if missing the Screening value MGADL, Muscle weakness, Fatigue scale, MGII, SFEMG: Predose Day 1.

██████████ BAFF=B-cell activating factor ; Ig=immunoglobulin; MGADL=myasthenia gravis-Activities of Daily Living; MGFA=Myasthenia Gravis Foundation of America; MGII= Myasthenia Gravis Impairment Index; SFEMG=single fiber electromyography; QMG=quantitative myasthenia gravis

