8.2 Statistical analysis of the secondary efficacy variables

The secondary efficacy variables are the changes from Baseline in MG-Composite and MGADL scores to Visit 9 (Day 29) prior to the first infusion of IMP in Dosing Period 2.

The MG-composite score comprises 10 items, each of which is weighted differently in the calculation of the overall score. The overall score ranges from 0 to 50, with a higher score indicating more severe disease. The items of MG-composite score will be displayed in a glossary. All individual item results will be listed. The total score will be listed and used to calculate change from baseline and used in descriptive summaries and for efficacy analysis. Total score will be used to determine responder state, which will be flagged in the listing and descriptively summarized.

The complete list of items and scores are provided in [Table 14-2](#).

The MGADL score comprises of 8 items, each with a score of 0 to 3. The items of MGADL will be displayed in a glossary. The total MGADL score ranges from 0 to 24 with a higher score indicating more disability. The complete list of items and scores are provided in [Table 14-3](#). The total score will be calculated according to the rules set down in [Section 14.3](#). All individual item results will be listed. The MGADL listing will contain total score for an interpolated visit at Day 57, where the total score is derived based on interpolation of Day 50 and 64. If total score on either day 50 or day 64 is not available no interpolated score will be derived. The total score after single item imputation will be listed and used to calculate change from baseline and used in descriptive summaries and for efficacy analysis, interpolated data from Day 57 will be part of the descriptive summary. Total score will be used to determine responder state, which will be flagged in the listing and descriptively summarized.

A comparison summary of MGADL showing absolute scores of Visit 9 (day 29), interpolated Day 57 and their differences will be presented by treatment group of second treatment period (Placebo - UCB7665 7mg/kg, Placebo - UCB7665 4mg/kg, UCB7665 7mg/kg - UCB7665 7mg/kg, UCB7665 7mg/kg - UCB7665 4mg/kg).

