8.3 Analysis of other efficacy variables

8.3.1 Summaries of efficacy variables

Values and change from Baseline in QMG, MG-Composite and MGADL at each scheduled visit will be descriptively summarized at each scheduled assessment during Treatment and Observation Periods. MGFA classification will be summarized during Treatment and Observation Periods.

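### Group 3's QMG change from Baseline at Visit 16 combines the placebo and active periods; the SAP plans a Visit 9-to-Day 57 difference for MGADL but not for QMG or MG-Composite

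*Protocol*

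**What the plan says.** **Supportive use.** Protocol 5.4.1, in the design rationale, states: "The comparison of the change from Baseline in QMG score at Visit 16 in Group 3 will strengthen analyses of the results". Those are Group 1's primary results. Group 3 receives three weekly placebo doses in Dosing Period 1 and three weekly 7mg/kg doses in Dosing Period 2.

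**Baseline.** SAP 3.3: "Baseline will be the last available predose value prior to the first infusion of study drug in Dosing Period 1". Protocol 14.2 uses the same anchor. Neither document defines a second reference value at Visit 9.

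**Timing.** Protocol 5.1 says the Visit 9 efficacy assessments "will therefore occur 2 weeks after the final dose of study drug in Dosing Period 1". Protocol 8.3.1 places them before rerandomization.

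**Planned tables.** SAP 1 says of itself: "It also defines the summary tables, figures and listings (TFLs) to be included in the final Clinical Study Report (CSR"). For MGADL, SAP 8.2 plans the following by the four sequences: "A comparison summary of MGADL showing absolute scores of Visit 9 (day 29), interpolated Day 57 and their differences". For all three scales, SAP 8.3.1 plans: "Values and change from Baseline in QMG, MG-Composite and MGADL at each scheduled visit will be descriptively summarized". SAP 8.1.1 and 8.2 add responder status. No section plans a Visit 9-to-Visit 16 difference for QMG or MG-Composite.

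**Inference.** Protocol 14.2 and SAP 3.1 restrict Dosing Period 2 to descriptive analysis.

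**The concern.** The protocol gives Group 3's Visit 16 result a purpose, which is to support the primary finding by showing what 7mg/kg does in subjects who first had placebo. The measure it names does not isolate that. Everything that happened to Group 3 on placebo between Day 1 and Day 29 is included in the Visit 16 change.

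Two things could make the placebo-period part non-zero: ordinary placebo response, and regression to the mean. Exclusion criterion 7 removes subjects with QMG below 11 at Baseline, so the Day 1 score is itself a selected value. A reader who sets Group 3's Visit 16 change beside Group 1's Visit 9 change would be comparing 56 days with 28, and could credit the drug with improvement that came before it.

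The SAP already uses the better-aligned difference for MGADL, the scale that has no Day 57 measurement. It does not use it for QMG, the primary scale, or MG-Composite, and gives no reason.

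**Working it through.** **1. The plan's own figure.** The last Dosing Period 1 dose is at Visit 6 (Day 15) and the primary assessment is at Visit 9 (Day 29). 29 − 15 = 14 days, which reproduces the stated 2 weeks.

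**2. Intervals from the nominal visit days.**

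| Interval | Arithmetic | Days | Treatment |
|---|---|---|---|
| Group 1, Baseline to Visit 9 | 29 − 1 | 28 | three 7mg/kg doses |
| Group 3, Baseline to Visit 9 | 29 − 1 | 28 | three placebo doses |
| Group 3, Visit 9 to Visit 16 | 57 − 29 | 28 | three 7mg/kg doses |
| Group 3, Baseline to Visit 16 | 57 − 1 | 56 | placebo, then 7mg/kg |

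The gap from the last Dosing Period 2 dose (Visit 13, Day 43) to Visit 16 is 57 − 43 = 14 days, the same as in step 1. Half of the Baseline-to-Visit 16 interval (28/56) is placebo. With the ±2-day visit windows the placebo segment runs 26 to 30 days and the active segment 24 to 32.

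**3. What the named measure contains.** For each subject in Group 3:

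change from Baseline at Visit 16 = (Visit 9 − Baseline) + (Visit 16 − Visit 9) = P + A

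where P is the placebo-period change and A the active-period change. The documents give neither. As an illustration, assume A = −3, equal in size to the change that SAP 8.1.1 calls clinically relevant, and vary P:

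| P (assumed) | P + A | Share arising on placebo | Visit 9 to Visit 16 |
|---|---|---|---|
| 0 | −3 | 0% | −3 |
| −1 | −4 | 25% | −3 |
| −2 | −5 | 40% | −3 |
| −3 | −6 | 50% | −3 |

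**4. Data available.** Table 5.1 and Protocol 8.3.1 and 8.4.2 schedule QMG and MG-Composite at both Visit 9 and Visit 16. MGADL is not scheduled at Visit 16, so SAP 8.2 interpolates Day 57 from Days 50 and 64; the midpoint is (50 + 64)/2 = 57.

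**5. What the planned tables leave out.** The variance of the paired difference is s9² + s16² − 2·r·s9·s16, where s9 and s16 are the SDs at the two visits and r is the Visit 9-to-Visit 16 correlation. The planned tables give SDs of the values and of the changes from Day 1, but not r. The paired SD therefore cannot be recovered from them.

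It is also unclear whether Visit 9 will be shown by sequence. SAP 2.3 says Dosing Period 2 "includes Visit 9, 10, 11, 12, 13, and 14", which points to the four sequence groups. SAP 3.2.2 starts Dosing Period 2 at its first actual dose and treats the pre-dose Day 29 assessments as completing Dosing Period 1. Under SAP 3.6 the Dosing Period 1 groups are placebo and 7mg/kg only.

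**6. Group size.** 42/4 = 10.5 randomized or 40/4 = 10 evaluable, so about 10 subjects in Group 3.

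**The case against.** **The mean is nearly available already.** The IRT "will stratify the rerandomization based on the treatment received in Dosing Period 1", so the placebo arm's Visit 9 mean is an unbiased stand-in for Group 3's own. The error in using about 20 subjects for 10 of them has SD s·√(1/10 − 1/20). For an assumed SD of change of 3, 4 or 5 points this is 0.67, 0.89 or 1.12 points. Individual scores are also listed (SAP 8.1.1), so the difference could be computed afterwards. This stands: what is missing from the tables is Group 3's own paired difference and its SD, not all information on it.

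**The sentence names no comparator.** If the Visit 16 change is to be set against the same subjects' Visit 9 change, the Day 1 anchor cancels and the active-period change remains. That is a fair reading, but it calls for exactly the paired difference that no section plans.

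**Period 2 is descriptive, and more can be added later.** Both are true. SAP 1 allows supplementary analyses under a separate plan after database lock. That limits the seriousness. It does not explain why MGADL has the table in advance and the primary scale does not.

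**Visit 9 to Visit 16 is not a second primary endpoint.** A reader might infer that this interval replicates the primary comparison. The documents do not support that. Duration, number of doses and the 14-day gap agree, but the primary result is a blinded contrast against placebo. Dosing Period 2 has no placebo arm, the Visit 9 score is not subject to the Baseline entry floor, and subjects who left during Dosing Period 1 are absent. For the two sequences that began on 7mg/kg, the Visit 9 value already follows three active doses.

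**Conclusion.** The point holds as a minor, no-cost improvement. For Group 3, change from Baseline at Visit 16 is a 56-day measure, half of it on placebo. The 28-day active-period difference is planned for MGADL only, although QMG and MG-Composite are measured directly at both visits. This rests on nominal visit days, the stated Baseline definition and the tables the SAP lists. The only assumed values are those in the illustration and in the approximation error above, and the conclusion does not depend on them.

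A reader might also infer that the primary result is compromised. It is not: the primary and secondary Visit 9 analyses use Dosing Period 1 data only. Nor do the documents show that any decision would change. With about 10 subjects in Group 3, the added summary would be imprecise, and its value lies in reporting the aligned difference and its SD openly.

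**What to change.** In SAP 8.3.1, add a descriptive summary of QMG and of MG-Composite showing the pre-dose Visit 9 value, the Visit 16 value and their within-subject difference with its SD, by the four treatment sequences, in the style already planned for MGADL. Then:

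- keep the tables of change from Day 1;
- state that Visit 9 is tabulated by sequence as well as by Dosing Period 1 group;
- state beside the table that Group 3's difference is an uncontrolled before-after change in about 10 subjects, not a placebo contrast.

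The same tables would also serve the descriptive Group 3 versus Group 4 comparison that Protocol 5.4.1 mentions. The cost is SAP wording and two descriptive tables, with no new data and no change to any test.
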